7.2 Full Analysis Set (FAS)

The FAS is defined as all patients who receive at least one dose of both investigational study drug and Nivolumab. The analyses of the primary and secondary efficacy endpoints will be performed using the FAS.

7.3 Clinical Activity Evaluable (CAE) Population

The CAE Population is defined as all patients who have received at least one dose of both investigational study drug and Nivolumab, have evaluable baseline tumor assessment and at least one post-baseline tumor assessment. This population will be used for the supportive analysis of tumor responses.

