Statistical Design Applied to CIT-Naïve with High PD-L1 Expression

The ORR using nivolumab in the population with non-squamous NSCLC having high PD-L1 expression is assumed to be 27% (p_0); thus this rate is considered uninteresting. The target ORR using the investigational agents in combination with nivolumab is 50% (p_1).

Stage 1 of enrollment will include approximately 17 evaluable patients. With exactly 17 evaluable patients at Stage 1, if at least 5 patients have Objective Responses, 27 additional evaluable patients will be enrolled, for a total sample size of 44 evaluable patients. If at least 18 Objective Responses are observed, further investigation may be warranted. If the true ORR is 27% (null hypothesis), the probability of early termination during the study is 0.50; the Type 1 error is equal to 0.0303 and the power is equal to 0.9018.

The exact stopping rules for all cohorts will be calculated based on the Predictive Probability Design, once the exact number of patients evaluable at Stage 1 is known. The aim is to get a minimum of 9 evaluable patients at Stage 1 for CIT-experienced and CIT-naïve with no/low PD-L1 expression cohorts and a minimum of 17 evaluable patients at Stage 1 for CIT-naïve with high PD-L1 expression cohort.

In order to be part of the clinical activity evaluable population, the patient must have at least one on-study disease assessment or discontinue from treatment for progressive disease prior to this assessment. Patients who discontinue treatment prior to the first on-study disease assessment for an AE, toxicity, or withdraw consent are considered non-evaluable for disease assessment. These patients will not be part of the clinical activity evaluable population.

[figure not shown]
Expansion Beyond Stage 2

[figure not shown]
The original protocol provided that if results in any strata were of high interest for efficacy, enrollment might be expanded to as many as 100 patients total in each cohort to narrow the 95% Confidence Interval (CI) around the ORR point estimate. Protocol Amendment 3 (Version 4.0) eliminates enrollment expansion beyond Stage 2 except in the sitravatinib segment of the study enrolling patients with CIT-experience.

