4.1 Inclusion Criteria

Patients must meet all of the following inclusion criteria as applicable for phase of the study to be eligible for enrollment into the study:

- 1. Histologically confirmed non-squamous NSCLC with metastatic or unresectable, locally advanced disease, not amenable to treatment with curative intent.
- 2. Receipt of at least one prior treatment in the advanced disease setting.
 - a) CIT-experienced: Most recent treatment must have included a checkpoint inhibitor (i.e., anti-PD-1 or anti-PD-L1 including nivolumab, pembrolizumab, durvalumab, atezolizumab or avelumab) with the result of progression of disease on or after treatment.

Note: For the PK sub-studies as outlined within Appendix 5 and Appendix 6, treatment with a checkpoint inhibitor (i.e., anti-PD-1 or anti-PD-L1) does not need to be included in the most recent treatment.

- b) CIT-naïve: Receipt of prior platinum-based doublet chemotherapy.
- 3. CIT-naïve: Molecular analysis of tumor sample collected following most recent therapy, assessed using the PD-L1 (28-8) CDx assay. Inclusion in the treatment arm will be based on documented no/low PD-L1 expression (positivity < 5% of tumor cells) or high PD-L1 expression (positivity ≥ 5% of tumor cells). *Note: This criterion does not apply to the PK sub-studies as outlined within Appendix 5 and Appendix 6.*
- 4. Measurable disease as per RECIST version 1.1.
- 5. Eastern Cooperative Oncology Group (ECOG) performance status 0, 1 or 2 (Appendix 1).
- 6. Adequate bone marrow and organ function demonstrated by:
 - Absolute neutrophil count $\geq 1,000/\text{mm}^3 \ (\geq 1.0 \times 10^9/\text{L})$
 - Platelet count $\ge 50 \times 10^9 / L \ (> 50,000 \text{ per mm}^3)$

- Alanine aminotransferase (ALT) and aspartate aminotransferase (AST)
 ≤ 2.5 × Upper Limit of Normal (ULN), or ≤ 5.0 × ULN for patients with documented liver metastases.
- Serum bilirubin $\leq 1.5 \times \text{ULN}$ or $\leq 3.0 \times \text{ULN}$ for patients with Gilbert Syndrome or documented liver metastases.
- Serum creatinine $\leq 1.5 \times ULN$.
- 7. \geq 18 years of age.
- 8. Women of child-bearing potential (WOCBP) or men whose partner is a WOCBP agrees to use contraception while participating in this study, and for a period of 6 months following termination of study treatment.
- 9. Completed informed consent process, including signing IRB/EC-approved informed consent form.
- 10. Willing to comply with clinical trial instructions and requirements.

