9.3 Analysis Populations

9.3.1 Modified Intent-to-Treat Population

The Modified Intent-to-Treat (mITT) population is defined as all patients who receive treatment with both an investigational study treatment and nivolumab on this study.

The primary efficacy analyses of the primary and secondary efficacy endpoints will be performed in the mITT population. In addition, the mITT population will be used in making decisions to expand the study to the next stage of enrollment.

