9.3.2 Clinical Activity Evaluable Population

In order to be considered eligible for the clinical activity evaluable population, the patient must have at least one on-study disease assessment or discontinue from treatment for progressive disease. Patients who discontinue treatment prior to the first on-study disease assessment for an AE, toxicity, or withdraw consent are considered non-evaluable for disease assessment and will not be part of the clinical activity evaluable population.

This population will be used to present tumor responses as well as to make decision on the Predictive Probability design.

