4.1.3 Analysis Populations

The modified Intent-to-Treat (mITT) population as defined in Section 9.3.1 of the protocol has been renamed as the Full Analysis Set (FAS).

Section 3.2 of the protocol described that for patients to be part of the Clinical Activity Evaluable (CAE) population they “...must have at least one on-study disease assessment or discontinue from treatment for progressive disease (PD) prior to this assessment.” This definition was modified by Mirati to be as described in Section 7.3 of this SAP, where it includes “patients with measurable disease (per RECIST 1.1) at baseline and have received at least one dose of both investigational study drug and Nivolumab, must have at least one on-study disease assessment or discontinue from treatment for PD.”

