10.0 Interim Analyses

There are no formal interim analyses in the study. Tumor responses will be reviewed for the CAE population to make decisions per the Predictive Probability Design on whether a cohort should be stopped for lack of tumor response as detailed in Section 6.2.

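### SAP 4.1.3 and SAP 7.3 define the Clinical Activity Evaluable population differently, and 7.3 can drop patients who stopped for progression from the supportive ORR and CBR

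*SAP*

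**What the plan says.** SAP 4.1.3 (Analysis Populations) reports that the protocol's CAE definition was modified "to be as described in Section 7.3 of this SAP, where it includes" patients with measurable disease at baseline and at least one dose of both drugs who "must have at least one on-study disease assessment or discontinue from treatment for PD".

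SAP 7.3, the section it points to, reads differently. Besides one dose of each drug, patients must "have evaluable baseline tumor assessment and at least one post-baseline tumor assessment". Discontinuation for PD is not an alternative.

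Protocol 3.2 requires "at least one on-study disease assessment or discontinue from treatment for progressive disease prior to this assessment", and Protocol 9.3.2 has the same alternative. Both protocol sections leave out patients who stop before the first assessment because of an adverse event, toxicity or withdrawn consent.

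The CAE population is used for the supportive ORR (SAP 11.1.6.1) and, alongside the FAS, for CBR (SAP 11.1.6.2.1). On stage decisions, Protocol 9.3.2 says "This population will be used to present tumor responses as well as to make decision on the Predictive Probability design" and SAP 10.0 says "Tumor responses will be reviewed for the CAE population to make decisions per the Predictive Probability Design", whereas Protocol 9.3.1 says "the mITT population will be used in making decisions to expand the study to the next stage of enrollment".

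**The concern.** The SAP gives two definitions for one population and presents them as the same. They part on patients who discontinue for PD with no post-baseline tumor assessment. These patients failed treatment. The protocol keeps them in the evaluable set and leaves out early stops for adverse event, toxicity or withdrawn consent. Section 7.3 removes that distinction, because everyone without a post-baseline assessment leaves the denominator.

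At stake is whether the supportive CAE rates are computed on a denominator from which known failures have been removed. The choice would fall to whoever programs the flag, possibly after results are known.

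**Working it through.** **1. The definitions side by side**

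| Source | Baseline requirement | After baseline | Stopped for PD, no assessment |
|---|---|---|---|
| Protocol 3.2, 9.3.2 | not stated in the definition | one on-study assessment, or stop for PD | included |
| SAP 4.1.3 | measurable disease | one on-study assessment, or stop for PD | included |
| SAP 7.3 | evaluable assessment | one post-baseline assessment | excluded |

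The difference between measurable and evaluable baseline disease has little practical effect, because inclusion criterion 4 already requires "Measurable disease as per RECIST version 1.1" (Protocol 4.1).

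**2. Direction of the effect**

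Let R be the number of responders, N the number evaluable under the 4.1.3 wording, and k the number who stopped for PD with no post-baseline assessment. None of the k can have a confirmed response or documented stable disease. The 4.1.3 rate is R/N and the 7.3 rate is R/(N − k). Since R/(N − k) ≥ R/N, ORR can only rise or stay equal. The same holds for CBR.

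**3. The plan's own figures**

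- Protocol Table 20, 25 of 125: Clopper-Pearson gives 20.0% (95% CI 13.4–28.1), as printed.
- Design with 9 then 17 patients (continue on ≥1 response, final ≥3): exact two-stage binomial gives alpha 0.0466 at 5% and power 0.9045 at 30%, as printed.
- Design with 17 then 44 patients (continue on ≥5, final ≥18): alpha 0.0303 at 27% and power 0.9018 at 50%, as printed.

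No printed figure is in dispute.

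**4. Illustrative size**

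The documents do not give k. The values of k below and the CBR numerator of 75 are assumptions. Given the limits set out under the objection, the one- and two-patient cases are the more plausible; the larger ones only show the range.

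| Quantity | 4.1.3 wording | k | 7.3 wording |
|---|---|---|---|
| ORR | 25/125 = 20.0% (13.4–28.1) | 2 | 25/123 = 20.3% (13.6–28.5) |
| ORR | same | 6 | 25/119 = 21.0% (14.1–29.4) |
| ORR | same | 13 | 25/112 = 22.3% (15.0–31.2) |
| ORR, stratum of 17 | 3/17 = 17.6% (3.8–43.4) | 1 | 3/16 = 18.8% (4.0–45.6) |
| ORR, stratum of 44 | 18/44 = 40.9% (26.3–56.8) | 1 | 18/43 = 41.9% (27.0–57.9) |
| CBR | 75/125 = 60.0% (50.9–68.7) | 2 | 75/123 = 61.0% (51.8–69.6) |
| CBR | same | 6 | 75/119 = 63.0% (53.7–71.7) |
| CBR | same | 13 | 75/112 = 67.0% (57.4–75.6) |

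**5. Stage decisions**

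Leaving out non-responders does not change the count of responses. With fixed thresholds and no refilling of the vacated places, alpha stays at 0.0466 and 0.0303. It would rise only if 7.3 governed the stage counts and those places were refilled. SAP 6.2 provides for replacement only when a patient leaves for a reason other than progression. The thresholds are in any case to be recalculated once the Stage 1 evaluable number is known. No breach of the 0.05 limit is claimed.

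**The case against.** The strongest reply is that the two wordings may select the same patients. Protocol 6.5 ties PD as a stopping reason to objective RECIST progression, which normally needs a scan, and lists global deterioration as a separate reason. Appendix 4 directs worsening without objective evidence to that separate code. A correctly coded PD discontinuation will therefore usually have a post-baseline assessment and satisfy 7.3. This stands as a limit on size. It does not remove the contradiction, because Protocol 3.2 expressly foresees discontinuation for PD before the first assessment.

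No result rests on the CAE population alone: ORR and CBR are also reported on the FAS, and SAP 11.1.1 tabulates the number in each population with discontinuation reasons, so a gap would be visible. That is correct, and it is why the point is minor.

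Protocol Section 9 lets the SAP modify the protocol's plans, so departing from the protocol is not in itself an error. That is also correct. But the change 4.1.3 declares is not the change 7.3 makes, so the loss of the PD clause is undisclosed.

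The contradiction could equally be removed by editing 4.1.3 to match 7.3. That would make the SAP consistent, but it would leave a supportive set that can only err upward and that departs from the protocol. Restoring the clause is the better choice.

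**Conclusion.** The concern holds and is minor. SAP 4.1.3 attributes to SAP 7.3 a definition that 7.3 does not contain, and following 7.3 can only raise the supportive CAE ORR and CBR or leave them unchanged. The number of affected patients is not in the documents and may be near zero. One or two such patients would move a rate by about 0.3 to 1.2 percentage points in the illustrations above.

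Not affected are the primary ORR (FAS, with unassessable patients counted as non-responders), CBR on the FAS, PFS (FAS), and DoR, since confirmed responders all have post-baseline assessments.

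No stage decision is shown to have been taken under 7.3. Glesatinib enrollment stopped in 2017, mocetinostat was never started, and the sitravatinib CIT-experienced expansion rested on June 2018 results, before this SAP, which is based on the February 2020 protocol. The documents do not date the decisions for the sitravatinib CIT-naïve strata.

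A separate wording point also holds: Protocol 9.3.1 names the mITT population for expansion decisions, while Protocol 9.3.2 and SAP 10.0 name the CAE.

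**What to change.** Rewrite SAP 7.3 to carry the definition quoted in SAP 4.1.3: at least one dose of both drugs, measurable disease at baseline, and either one on-study disease assessment or discontinuation for PD, with the latter counted as non-response. SAP 4.0 provides for a final version before database lock, which is the place to do it.

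Separately, name one population for the Predictive Probability Design decisions by reconciling Protocol 9.3.1 with Protocol 9.3.2 and SAP 10.0. Recording the choice in SAP 4.1 would be the lightest route; editing the protocol itself would go through the change process in Protocol 13.1.

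The cost is one sentence, one population flag and one clarification of the decision population. No new data are needed. The supportive CAE ORR and CBR may come out slightly lower than under 7.3, or unchanged.

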7.4 Safety Population

The Safety Population is defined as all patients who received at least 1 dose of either investigational study drug or Nivolumab. The Safety Population will be used for all safety analyses.

7.5 DLT Evaluable Population

The DLT evaluable population is defined as any patient who is enrolled in a cohort in the lead-in phase of the study and who either has been on study for one full cycle and has received treatment with Nivolumab and at least 75% of scheduled investigational study treatment doses in Cycle 1 or who has experienced a DLT in Cycle 1.

7.6 PK Sub-Study Population

The PK sub-study population is defined as any patient consenting to be part of either the PK formulation or the PK food effect sub-studies. Consent will be identified programmatically from the Study Treatment Assignment page of the CRF.

8.0 Endpoint Definitions

8.1 Baseline Characteristics

8.1.1 Baseline

Baseline is defined as the last non-missing value prior to first dose. In most cases this will be Cycle 1 Day 1, however values from the Screening/Baseline visit may be used if Cycle 1 Day 1 is missing, or after first dose.

8.1.2 Age

Age (years) is calculated relative to the date of signing informed consent;

$$\text{Age (years)} = (\text{Date of Informed Consent} - \text{Date of Birth}) + 1 / 365.25.$$

8.1.3 Time Since Diagnosis

Time since diagnosis is calculated relative to the date of first dose of any study drug. Missing or partial dates of diagnosis will not be imputed.

$$\text{Time Since Diagnosis (Years)} = (\text{Date of First Dose} - \text{Date of Diagnosis}) + 1/365.25.$$

8.2 Efficacy Variables

With regard to efficacy endpoints, the term “on-study” includes the period from the first dose of any study drug until the end of study. The term “baseline” will include screening and Cycle 1 Day 1 pre-dose assessment which would represent a 29-day window. Unscheduled visits assessments preceding Cycle 1 Day 1 will be also considered for baseline.

Disease assessments involving radiographic evaluations may be performed over the course of a few days. The date of response (CR, PR, SD, PD or Not Evaluable [NE]) will be recorded as the date of the last radiographic evaluation included in the series for that time point assessment. For the investigator assessment, the date will be determined using the latest Date of Assessment recorded among the radiologic modalities included for the applicable Time Point Assessment.

8.2.1 Objective Response Rate (ORR)

Objective disease response will be categorized in accordance with RECIST v1.1. ORR is defined as the proportion of patients documented to have a confirmed CR or PR. ORR as reported by the investigator will be used in decision making for study expansion (Predictive Probability Design).

Best Overall Response (BOR) is defined as the best response among all overall responses (in the order CR, PR, SD, PD then NE) recorded from the start of study drug until disease progression/recurrence or start of subsequent anti-cancer therapy, whichever comes first. The status of best response of CR or PR must be confirmed by repeat tumor assessment within no less than 4 weeks according to RECIST v1.1. If the status of CR or PR cannot be confirmed by repeat tumor assessment, the BOR of unconfirmed CR and PR will be SD or NE. The status of BOR of SD requires an on-study assessment after at least 42 days from first dose date of treatment.

**Confirmed Response Based on Subsequent Assessments*;**

First Time Point Response**	Second Time Point Response	Confirmed Response (Best Response)*
PD	No further evaluation	PD
NE	PD	PD
CR	PD	SD or PD (1)
PR	PD	SD or PD (1)
SD	PD	SD or PD (1)
CR	CR	CR
CR	NE **	SD or NE (2)
PR	CR	PR
PR	PR	PR
PR	SD (3)**	SD
PR	NE **	SD or NE (2)
SD	CR	SD
SD	PR	SD
SD	SD	SD
SD	NE	SD or NE (2)
NE	CR	SD
NE	PR	SD
NE	SD	SD
NE	NE	NE

* A Best Response of SD can only be made after the patient is on-study for a minimum of 42 days. If the patient is on-study less than 42 days, any tumor assessment indicating stable disease before this time period will have a Best Response of NE unless PD is identified.

** Subsequent documentation of CR may provide confirmation of a previously identified CR for patients where the second integrated response was NE. Subsequent documentation of PR may provide confirmation of a previously identified PR for patients where the second integrated response was NE or SD. If the third response confirms the CR (or PR) then the confirmed response will be CR (or PR).
For example: CR NE CR = CR; PR NE PR = PR.

Additionally, one SD is allowed between PRs (e.g., PR SD PR = PR).

- (1) Best response will be SD if the first response is after 42 days on-treatment. Otherwise, the best response will be PD.
- (2) Best response will be SD if the first response is after 42 days on-study. Otherwise, the best response will be NE.
- (3) Response is SD if the increase from the first to the second assessment does not qualify for PD.

For patients with unconfirmed CR/PR that can't be confirmed due to dropping off study, the best overall response will be SD.

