8.4 Safety Variables

With regard to safety summaries, the term “on-treatment” is the period from first dose until either last dose + 28 days or the start of anti-cancer therapy, whichever is earlier.

AEs, laboratory values and ECGs will be graded according to the NCI CTCAE v4.03 (see Section 13.0 for link to the criteria), ECGs will also be graded according to International Conference on Harmonisation (ICH) E14.

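### SAP 8.2.1 states the 42-day minimum for stable disease inconsistently, leaving best response and clinical benefit undetermined for a few patients who stop or drop off early

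*SAP*

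**What the plan says.** The minimum appears in five forms in SAP 8.2.1:

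- **Main text:** "The status of BOR of SD requires an on-study assessment after at least 42 days from first dose date of treatment". It also says that an unconfirmed CR or PR becomes SD or NE.
- **Footnote \*** to the confirmed-response table: "A Best Response of SD can only be made after the patient is on-study for a minimum of 42 days". It adds that SD seen in a patient with less time on study is NE unless PD is found.
- **Footnote (1)**, attached to CR, PR or SD followed by PD: "Best response will be SD if the first response is after 42 days on-treatment. Otherwise, the best response will be PD".
- **Footnote (2)**, attached to CR, PR or SD followed by NE: "Best response will be SD if the first response is after 42 days on-study. Otherwise, the best response will be NE".
- **Closing sentence**, on an unconfirmed CR or PR that cannot be confirmed "due to dropping off study, the best overall response will be SD". It gives no minimum time.

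Two definitions bear on these. SAP 8.2 says that for efficacy the on-study period "includes the period from the first dose of any study drug until the end of study". SAP 8.4 says that on-treatment, for safety summaries, "is the period from first dose until either last dose + 28 days or the start of anti-cancer therapy, whichever is earlier". There is no efficacy definition of on-treatment.

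Protocol Appendix 4 requires, for SD, an assessment after six weeks or more on treatment, and reports unconfirmed CR or PR as SD.

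SAP 8.2.3 counts confirmed CR, confirmed PR and SD as clinical benefit and states no duration. SAP 4.1.4 replaces the two assessments and 14 weeks of Protocol 9.4.2 with a single assessment at 42 days, and refers to 8.2 for the definition.

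**The concern.** With the protocol's 14-week requirement gone, the 42-day rule in 8.2.1 is the only floor on SD within CBR. BOR is tabulated beside the primary variable by treatment arm and stratum (SAP 11.1.6.1), and CBR is reported in both the FAS and the CAE population (11.1.6.2.1). If the floor can be read in more than one way, two programmers working faithfully from the SAP could put the same patient in different BOR categories and report different CBRs. The patients concerned are mainly those who stop early, for whom it matters most whether they count as having benefited.

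**Working it through.** The plan gives no figure for this point, so the check sets the rules against one another.

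**Notation.** *s* is days from first dose to the first response assessment. *L* is days from first dose to last dose of study treatment.

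**Rules.**
- Main text: SD allowed if s ≥ 42.
- Footnote (2): s > 42, because on-study time starts at first dose (SAP 8.2).
- Footnote (1), with on-treatment as in SAP 8.4: min(s, L + 28) > 42.
- Footnote (1), with on-treatment as dosing days only: min(s, L) > 42. No document states this reading.
- Footnote \*: the patient's total time on study is at least 42 days, whatever the scan date.
- Closing sentence: no condition.

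**Scheduled first scan.** Scans are every 8 weeks ± 10 days from Cycle 1 Day 1 (disease-evaluation footnote to Table 1 in both documents). So 8 × 7 = 56, and the window is 56 − 10 = 46 to 56 + 10 = 66 days.

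**Step 1: main text against footnote (2).** They differ only at s = 42 exactly (at least 42 versus after 42). For s from 46 to 66 they never disagree.

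**Step 2: patient still dosing at the scan (L = s).** Both readings of footnote (1) reduce to s > 42. Every in-window scan passes, and all rules agree.

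**Step 3: patient who stopped early, in-window scan, then PD.** Under the 8.4 definition, footnote (1) fails when L + 28 ≤ 42, that is L ≤ 14. Under dosing days only it fails when L ≤ 42. In those cases footnote (1) gives PD where the main text allows SD.

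Example: both drugs stopped on Day 12, no new anti-cancer therapy, SD on Day 57, PD on Day 113.
- Main text: the Day 57 scan is 56 days after first dose, and 56 ≥ 42, so SD.
- Footnote (1) with 8.4: on-treatment ends on Day 12 + 28 = Day 40, short of 42, so PD.

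By contrast, a patient who stops on Day 30 is on-treatment to Day 58 and passes.

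**Step 4: unconfirmed CR or PR, then drop-off.**
- For s from 46 to 66, the main text and the closing sentence both give SD.
- For an off-schedule scan with s < 42 and no later assessment, the main text excludes SD and leaves NE. The closing sentence gives SD. Footnote (2), the nearest tabulated case, also gives NE.

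**Step 5: effect per patient.** PD and NE both count as no benefit, so each patient moved into or out of SD shifts CBR by 100/n points:

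| n | Shift in CBR (points) |
|---|---|
| 17 | 100/17 = 5.9 |
| 44 | 100/44 = 2.3 |
| 125 | 100/125 = 0.8 |

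ORR counts only confirmed CR and PR, so it does not move.

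**The case against.** The best defence is that this is uneven wording around a single intention. All the terms start at first dose. On-treatment is defined for safety alone, so footnote (1) can be taken to mean 42 days after treatment began, echoing Protocol Appendix 4. Footnote \* states a necessary condition, not a sufficient one, and the main text still applies beside it. The schedule puts first scans at 46 days or later, so few patients could be touched. CBR is secondary and descriptive, with no test.

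Most of this stands, and it rules out several stronger readings that a reader might infer:

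- *Three separate clocks.* SAP 8.2 starts on-study time at first dose, so that rule and the from-first-dose rule share one start. On-treatment differs only in where it ends.
- *The clock decides between PD and NE.* Footnote (1) applies when the second response is PD and footnote (2) when it is NE. That fallback is set by the second scan, by design.
- *An early SD scan qualifies if the patient is merely followed up.* Footnote \* alone would not exclude it, but the main text does.
- *A shift of several points in CBR across the trial.* One could assume that 5% of patients (range 2 to 10%) stop both drugs before Day 42, have SD and later progress, and so obtain about 5 points (2 to 10). That needs the dosing-days reading. With last dose + 28 days, only stops by about day 14 count. No document supports the percentages.

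The defence does not remove two conflicts. Footnotes (1) and (2) sit next to each other and use different terms, so a programmer cannot assume they mean the same, and the only written definition of on-treatment leads to PD in the Step 3 example. The closing sentence assigns SD outright where the main text says SD or NE.

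**Conclusion.** The inconsistency is real and narrow. The text leaves BOR, and therefore CBR, undetermined for two groups:

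- patients with an unconfirmed CR or PR on a scan earlier than 42 days who then drop off (SD or NE);
- patients who stop both drugs early, start no new therapy, have CR, PR or SD at the first scan and then PD (SD or PD). With the 8.4 definition this means a last dose by about day 14.

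The at-least versus after wording adds a mismatch at exactly day 42. Per-patient effects are those in Step 5. The total cannot be computed, because the documents do not give the number of early stoppers or early off-schedule scans. The primary endpoint is not affected. The point merits correction because this rule is the only remaining floor for SD in CBR, not because a large error is expected.

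**What to change.** State one rule in SAP 8.2.1 and use it in the main text, footnotes \*, (1) and (2), and the closing sentence: SD requires a time-point assessment of CR, PR or SD dated at least 42 days after first dose. Otherwise best response is PD if the next assessment is PD, and NE if it is not. Use the same inequality throughout, and remove on-treatment and on-study from the 42-day tests. Change the closing sentence to: SD if that assessment is at least 42 days after first dose, otherwise NE. Add a line stating that the six weeks on treatment in Protocol Appendix 4 is counted from first dose to the assessment date.

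The cost is SAP wording only. SAP 4.0 provides for a final version before database lock, and the primary endpoint definition is untouched. There are two consequences to accept openly: a few early-scan patients become NE, and a few early stoppers who could have been read as PD become SD and count towards CBR.
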